# **10.2** Assessment of relationship

Adverse events will be recorded in the EMR and transferred to Prometheus using a recognized medical term or diagnosis that accurately reflects the event. Adverse events will be assessed by the investigator for severity, relationship to the investigational product, possible etiologies, and whether the event meets criteria of an SAE and therefore requires immediate notification to AstraZeneca/MedImmune Patient Safety.

The following variables will be collected for each AE:

- AE (verbatim)
- The date when the AE started and stopped
- Changes in NCI CTCAE grade and the maximum CTC grade attained
- Whether the AE is serious or not
- Investigator causality rating against the IPs (yes or no)
- Action taken with regard to IPs
- Administration of treatment for the AE
- Whether the AE caused the patient's withdrawal from the study (yes or no)
- Outcome

In addition, the following variables will be collected for SAEs as applicable:

- Date AE met criteria for serious AE
- Date Investigator became aware of serious AE
- AE is serious due to criteria
- Date of hospitalization
- Date of discharge
- Probable cause of death
- Date of death
- Autopsy performed
- Description of AE
- Causality assessment in relation to Study procedure(s)
- Causality assessment in relation to Additional Study Drug

Events, which are unequivocally due to disease progression, should not be reported as an AE during the study.

# 10.3 Study recording period and follow-up for adverse events and serious adverse events

Adverse events and serious adverse events will be recorded from time of signature of informed consent, throughout the treatment period and including the follow-up period (90 days after the last dose of durvalumab + tremelimumab).

During the course of the study, all AEs and SAEs should be proactively followed up for each subject. Every effort should be made to obtain a resolution for all events, even if the events continue after discontinuation/study completion.

If a subject discontinues from treatment for reasons other than disease progression, and therefore continues to have tumor assessments (per Table 2), drug or procedure-related SAEs must be captured until the patient is considered to have confirmed PD and will have no further tumor assessments.

The investigator is responsible for following all SAEs until resolution, until the subject returns to baseline status, or until the condition has stabilized with the expectation that it will remain chronic, even if this extends beyond study participation.

# Follow-up of unresolved adverse events

Any AEs that are unresolved at the subject's last visit in the study are followed up by the investigator for as long as medically indicated, but without further recording in Prometheus. After 90 days, only subjects with ongoing investigational product-related SAEs will continue to be followed for safety.

AstraZeneca/MedImmune retains the right to request additional information for any subject with ongoing AE(s)/SAE(s) at the end of the study, if judged necessary.

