- Unless otherwise noted, the electronic SAE application (eSAE) will be utilized for safety reporting to the IND Office and MDACC IRB.
- Serious adverse events will be captured from the time of the first protocol-specific intervention, until 90 days after the last dose of study drug, unless the participant withdraws consent. Serious adverse events must be followed until clinical recovery is complete and laboratory tests have returned to baseline, progression of the event has stabilized, or there has been acceptable resolution of the event.
- Additionally, any serious adverse events that occur after the 90 day time period that are related to the study treatment must be reported to the IND Office. This may include the development of a secondary malignancy.

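### The post-90-day limit on safety follow-up conflicts with the duty to follow every SAE, and the bar on later database entry can leave the final safety table out of date

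*Combined protocol and SAP*

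**What the plan says.** Three places in the protocol govern adverse events that are still open when a man leaves the study.

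- Section 10.3, main text. AEs and SAEs are recorded from consent to 90 days after the last dose. For all events: "Every effort should be made to obtain a resolution for all events, even if the events continue after discontinuation/study completion". For serious ones: "The investigator is responsible for following all SAEs until resolution, until the subject returns to baseline status", or until the condition is stable and expected to be chronic, "even if this extends beyond study participation". For men who stop treatment for reasons other than progression, "drug or procedure-related SAEs must be captured until the patient is considered to have confirmed PD".
- Section 10.4, SAE reporting for institution-sponsored IND protocols. "Serious adverse events must be followed until clinical recovery is complete and laboratory tests have returned to baseline", with stabilization or acceptable resolution as alternative end points.
- Section 10.3, subsection on follow-up of unresolved adverse events. AEs open at the last visit are followed "for as long as medically indicated, but without further recording in Prometheus". The next sentence reads: "After 90 days, only subjects with ongoing investigational product-related SAEs will continue to be followed for safety".

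Section 12.3 names Prometheus as the electronic case report form and sends all adverse events there. Section 10.2 lists what is collected for each event, including stop date, outcome and "Changes in NCI CTCAE grade and the maximum CTC grade attained". Section 11.2.1 tabulates events at the end of the trial, once per patient, at the highest grade and with the final attribution. That table serves the primary objective in section 2.1, safety and tolerability.

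**The concern.** Two rules in the unresolved-events subsection do not fit the rest of the protocol.

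The first is who is followed. The main text of section 10.3 and section 10.4 set a duty for every SAE with no limit by cause or time. The 90-day sentence keeps only men with an open SAE attributed to the product. Site staff who apply it as written would stop following a man whose only open SAE is called unrelated, or is attributed to a procedure. Attribution can change as an event develops, and this matters for immune-mediated toxicity, where late recognition is plausible.

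The second is what is recorded. Clinical follow-up may continue after the last visit, but its results may not be entered in the case report form. The final safety table calls for a final attribution and a highest grade, and either may be settled only after that visit.

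**Working it through.** No sample size, power or error rate enters this point, so the check sets the provisions side by side. The sentence does not say what its 90 days run from. I assume the last dose, as in the recording periods of sections 10.3 and 10.4.

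**Step 1. Who is followed after 90 days.** Take an event still open and not stable at that time, in a man with no other open event.

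| Event | 10.3 main text | 10.4 | 90-day sentence |
|---|---|---|---|
| SAE related to product | followed | followed | followed |
| SAE related to procedure only | followed | followed | not followed |
| SAE called unrelated | followed | followed | not followed |
| Non-serious AE | resolution sought | not covered | not followed |

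The provisions agree on the first row only. Rows two and three are the conflict over SAEs. Row two also sits badly with the extended capture rule in section 10.3, which names procedure-related as well as drug-related SAEs. Row four conflicts inside the subsection itself, because its first sentence keeps open AEs under follow-up while there is a medical need. The subsection on post-study events does not settle the matter. It concerns new events, and SAEs the investigator hears of and thinks may be related, not an open SAE already called unrelated.

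**Step 2. What reaches the final table.** Follow an AE open at the last visit whose grade or attribution later changes.

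- Non-serious and stays so: followed clinically, with Prometheus closed. No other reporting route is described beyond the company's option to ask for information.
- Non-serious, then serious: section 10.4.2 passes this to the company and the FDA.
- Serious: section 10.4 sends it to the IND Office whatever its attribution, through eSAE. Related SAEs after the window are also reported.

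None of these provisions says that the update is carried into the section 11.2.1 table. The exposure is therefore greatest for AEs that stay non-serious and for SAEs still called unrelated.

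**Step 3. The stopping rule.** Section 11.2.1 counts grade 3 or higher related events in the first 8 weeks. A steroid-treatable event counts only if it fails to improve to grade 1 or better within 2 weeks of steroids. With prompt steroids:

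- latest day the status is known = 8 × 7 + 2 × 7 = 56 + 14 = day 70 after the first dose
- the section 10.3 recording period ends 90 days after the last dose, so no earlier than day 90 after the first dose
- slack = 90 − 70 = 20 days or more

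The status is settled inside the recording period.

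**The case against.** The strongest reply is that the provisions can be read together. The 90-day sentence speaks of subjects in study follow-up. Sections 10.3 and 10.4 speak of events, and section 10.3 says its duty outlasts participation. On that reading no SAE is abandoned. This is a fair reading, and it means the text does not prove that follow-up is lost. But the protocol does not draw the distinction, and the word that limits follow-up to product-related SAEs carries no such qualifier.

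The second reply is that closing the case report form at the last visit is an ordinary data cut-off. The company may ask for more on events open at the end of the study, and the final table is descriptive, in at most 27 men, with no formal hypotheses (section 11.3). All of that is true and limits the weight of the point. A cut-off at each man's last visit still does not match a table defined by final attribution, and the company's right to ask is optional.

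A reader might go further and infer that the stopping rule is at risk: a man leaves early with a steroid-treated grade 3 event open, and whether it improved is never entered. The documents do not support this. Section 10.3 records events to 90 days after the last dose. Section 11.2.4 requires information on patients already reported to be updated with every monitoring report. Section 4.3 offers telephone follow-up to men who will not return. Table 3 generally calls for prompt steroids at grade 3 or 4. Where consent is withdrawn or contact is lost, the missing information is not caused by the database rule.

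**Conclusion.** The point holds as a conflict of wording and a limited recording gap. Read literally, the 90-day sentence removes from follow-up SAEs that are unrelated or only procedure-related and still open after 90 days, against sections 10.3 and 10.4. The Prometheus bar means the section 11.2.1 table may carry a superseded grade or attribution for events open at the last visit.

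The size is modest. The documents give no basis for counting affected events. With enrollment capped at 27, the number is probably small, though each record is visible in a table of that size. The effect is confined to a descriptive table, and the toxicity stopping rule stands. The conclusion assumes that the 90 days run from the last dose and that eSAE updates are not carried into the table by some process the protocol leaves unstated. If such a process exists, the recording gap shrinks to AEs that remain non-serious. It would be too strong to say that safety data will be lost or that a wrong grade will be reported.

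**What to change.** 1. Delete the 90-day sentence, or reword it to match sections 10.3 and 10.4: all SAEs, whatever the attribution, followed to resolution, baseline or chronic stability. If a limit on study visits for each subject is intended, state it separately and say what the 90 days run from.
2. For AEs with onset inside the existing 90-day window, allow outcome, maximum grade and final attribution to be updated in Prometheus until database lock, reconciled with eSAE.
3. In the section 11.2.1 table, show events still open at lock as ongoing.

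The cost is an edit to the protocol text and a few late updates to existing AE records. No visit is added and the onset window is not widened.

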### Post study events

After the subject has been permanently withdrawn from the study, there is no obligation for the investigator to actively report information on new AE or SAEs occurring in former studysubjects after the 90-day safety follow-up period for patients treated with durvalumab + tremelimumab. However, if an investigator learns of any SAEs, including death, at any time after the subject has been permanently withdrawn from study, and he/she considers there is a reasonable possibility that the event is related to study treatment, the investigator should notify the study sponsor and AstraZeneca/MedImmune Drug Safety.

# **10.4** Reporting of Serious Adverse vents

## Serious Adverse Event (SAE) Reporting for MD Anderson-sponsored IND Protocols

An adverse event or suspected adverse reaction is considered "serious" if, in the view of either the investigator or the sponsor, it results in any of the following outcomes:

- Death
- A life-threatening adverse drug experience any adverse experience that places the patient, in the view of the initial reporter, at immediate risk of death from the adverse experience as it occurred. It does not include an adverse experience that, had it occurred in a more severe form, might have caused death.
- Inpatient hospitalization or prolongation of existing hospitalization
- A persistent or significant incapacity or substantial disruption of the ability to conduct normal life functions.
- A congenital anomaly/birth defect.

Important medical events that may not result in death, be life-threatening, or require hospitalization may be considered a serious adverse drug experience when, based upon appropriate medical judgment, they may jeopardize the patient or subject and may require medical or surgical intervention to prevent one of the outcomes listed in this definition. Examples of such medical events include allergic bronchospasm requiring intensive treatment in an emergency room or at home, blood dyscrasias or convulsions that do not result in inpatient hospitalization, or the development of drug dependency or drug abuse (21 CFR 312.32).

- Important medical events as defined above, may also be considered serious adverse events. Any important medical event can and should be reported as an SAE if deemed appropriate by the Principal Investigator or the IND Sponsor, IND Office.
- All events occurring during the conduct of a protocol and meeting the definition of a SAE must be reported to the IRB in accordance with the timeframes and procedures outlined in "The University of Texas MD Anderson Cancer Center Institutional Review Board Policy for Investigators on Reporting Unanticipated Adverse Events for Drugs and Devices". Unless stated otherwise in the protocol, all SAEs, expected or unexpected, must be reported to the IND Office, regardless of attribution (within 5 working days of knowledge of the event).
- All life-threatening or fatal events, that are unexpected, and related to the study drug, must have a written report submitted within 24 hours (next working day) of knowledge of the event to the Safety Project Manager in the IND Office.

- Unless otherwise noted, the electronic SAE application (eSAE) will be utilized for safety reporting to the IND Office and MDACC IRB.
- Serious adverse events will be captured from the time of the first protocol-specific intervention, until 90 days after the last dose of study drug, unless the participant withdraws consent. Serious adverse events must be followed until clinical recovery is complete and laboratory tests have returned to baseline, progression of the event has stabilized, or there has been acceptable resolution of the event.
- Additionally, any serious adverse events that occur after the 90 day time period that are related to the study treatment must be reported to the IND Office. This may include the development of a secondary malignancy.

# 10.4.1 Reporting to FDA

• Serious adverse events will be forwarded to FDA by the IND MD Anderson (Safety Project Manager IND Office) according to 21 CFR 312.32.

It is the responsibility of the PI and the research team to ensure serious adverse events are reported according to the Code of Federal Regulations, Good Clinical Practices, the protocol guidelines, the sponsor's guidelines, and Institutional Review Board policy.

# 10.4.2 Investigator Communication with Supporting Companies

All SAEs will be reported, whether or not considered causally related to the investigational product, or to the study procedure(s). The reporting period for SAEs is 90 days after the last dose of durvalumab + tremelimumab or until the initiation of alternative anticancer therapy. The investigator and/or Sponsor are responsible for informing the Ethics Committee and/or the Regulatory Authority of the SAE as per local requirements.

The investigator and/or sponsor must inform the FDA, via the M.D. Anderson SAE form, of any serious or unexpected adverse events that occur in accordance with the reporting obligations of 21 CFR 312.32, and will concurrently forward all such reports to AstraZeneca. A copy of the M.D. Anderson SAE form must be faxed to AstraZeneca at the time the event is reported to the FDA. It is the responsibility of the sponsor to compile all necessary information and ensure that the FDA receives a report according to the FDA reporting requirement timelines and to ensure that these reports are also submitted to AstraZeneca at the same time.

- \* A *cover page* should accompany the M.D. Anderson SAE form indicating the following:
  - "Notification from an Investigator Sponsored Study"

- The investigator IND number assigned by the FDA
- The investigator's name and address
- The trial name/title and AstraZeneca ISS reference number (ESR-15-11590)
- \* Sponsor must also indicate, either in the SAE report or the cover page, the *causality* of events *in relation to all study medications* and if the SAE is *related to disease progression*, as determined by the principal investigator.
- \* Send SAE report and accompanying cover page by way of email to AstraZeneca's designated mailbox: [contact]
  - If a non-serious AE becomes serious, this and other relevant follow-up information must also be provided to AstraZeneca and the FDA.
  - Serious adverse events that do not require expedited reporting to the FDA still need to be reported to AstraZeneca using the MD Anderson form for serious adverse events. This information should be reported on a monthly basis and under no circumstance less frequently than quarterly.

# 10.4.3 Reporting of deaths

All deaths that occur during the study, or within the protocol-defined 90-day post-last dose of durvalumab + tremelimumab safety follow-up period must be reported as follows:

- Death that is clearly the result of disease progression should be documented but and be reported as an SAE.
- Where death is not due (or not clearly due) to progression of the disease under study, the AE causing the death must be reported to as a SAE within **24 hours**. The report should contain a comment regarding the co-involvement of progression of disease, if appropriate, and should assign main and contributory causes of death.
- Deaths with an unknown cause should always be reported as a SAE.

Deaths that occur following the protocol-defined 90-day post-last-dose of Durvalumab safety follow-up period will be documented as events for survival analysis, but will not be reported as an SAE.

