# 10.5.4 Disease progression

Disease progression can be considered as a worsening of a patient's condition attributable to the disease for which the IP is being studied. It may be an increase in the severity of the disease under study and/or increases in the symptoms of the disease. The development of new or progression of existing metastasis to the primary cancer under study should be considered as diseaseprogression and not an AE. Events that are unequivocally due to disease progression should not be reported as an AE during the study

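### Section 10.4.3 excludes every death after day 90 from SAE reporting, while Sections 10.3 and 10.4 call for treatment-related ones to be reported

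*Combined protocol and SAP*

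**What the plan says.** **Deaths after day 90.** The last sentence of Section 10.4.3 covers deaths later than 90 days after the last durvalumab dose. They "will be documented as events for survival analysis, but will not be reported as an SAE". Nothing in the sentence separates related from unrelated deaths.

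**Related SAEs after day 90.** Section 10.4 treats an event as serious if "in the view of either the investigator or the sponsor, it results in any of the following outcomes", and death heads the list that follows. For later events the same section says that those that "occur after the 90 day time period that are related to the study treatment must be reported to the IND Office". Under Post study events, Section 10.3 covers the investigator who "learns of any SAEs, including death, at any time after the subject has been permanently withdrawn from study": if a link to study treatment is reasonably possible, both the sponsor and the supporting company should be told. Section 10.3 also keeps capture of drug- or procedure-related SAEs open until confirmed progression for patients who stop treatment for another reason.

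**The reporting window itself.** Section 10.3 records AEs and SAEs from consent through treatment, "including the follow-up period (90 days after the last dose of durvalumab + tremelimumab". Section 10.4 captures SAEs from the first protocol-specific intervention to 90 days after the last dose of study drug, and only withdrawal of consent shortens that. Section 10.4.2 says: "The reporting period for SAEs is 90 days after the last dose of durvalumab + tremelimumab or until the initiation of alternative anticancer therapy".

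**Deaths from progression.** The first bullet of Section 10.4.3 has two conjunctions in a row, and it is unclear whether such deaths are or are not to be reported as SAEs. Section 10.5.4 says: "Events that are unequivocally due to disease progression should not be reported as an AE during the study". Section 10.2 says the same.

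**The concern.** Section 10.4.3 is the section dedicated to deaths, so it is where site staff would look when one occurs. Section 4.3 has all subjects followed for survival and Table 2 schedules survival contacts beyond the 3-month visit, so the site will hear of late deaths. If staff follow Section 10.4.3 as written, a late fatal immune-mediated event would be logged as a survival event and would not be sent on as an SAE.

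The primary objective is safety and tolerability (Section 2.1), and Section 11.2.1 tabulates all adverse events at the end of the trial. With maximum enrollment of 27, one death is 1/27 = 3.7% of patients. Whether a related late death reaches the IND Office and the supporting company should not depend on which paragraph is consulted.

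**Working it through.** The plan states no figure that could be recomputed here. The check sets the rules side by side and applies them to two test cases.

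**Case A: treatment-related death on day 120 after the last dose** (120 − 90 = 30 days past the window).

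| Place | Instruction |
|---|---|
| 10.4, definition of serious | Death is a serious outcome, so the event is an SAE |
| 10.4, events after 90 days | Must go to the IND Office |
| 10.3, Post study events | Sponsor and supporting company should be notified, if the patient has left the study |
| 10.3, patients off treatment without progression | Related SAE still captured until confirmed progression |
| 10.4.3, last sentence | Not reported as an SAE |

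The last row contradicts the others, and no wording in Section 10.4.3 yields to them.

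**Case B: SAE on day 60, with new anticancer therapy started on day 40.** Both days are inside the 90-day window. Sections 10.3 and 10.4 have it recorded and reported. Under Section 10.4.2 the period closed on day 40 if the two limits mean the earlier one, and is still open if they mean the later one; the section does not say which. If the event is fatal, Section 10.4.3 also requires it to be reported, because its rule for deaths within 90 days has no stop at new therapy. This is an ambiguity rather than a flat contradiction.

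**Effect on the stopping rule.** TOX counts events in the first 8 weeks of therapy (Section 11.2.1), which is 8 × 7 = 56 days. A death more than 90 days after the last dose is also more than 90 days after the first, so it cannot be a TOX event. In Case B the recording rule in Section 10.3 has no stop at new therapy. The Table 4 boundaries are unaffected.

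**Anchor of the 90-day clock.** Sections 10.3 and 10.4.2 and the opening of 10.4.3 name the two drugs together, the last sentence of 10.4.3 names durvalumab alone, and 10.4 says study drug. Under the full schedule in Table 1 the last combination dose is at week 12 and the last durvalumab dose at week 48. If the paired wording meant the last combination dose, the window would close at week 12 + 90/7 = 12 + 12.9 = 24.9, in the middle of treatment. Section 10.3 records events throughout treatment, Table 1 has AE/SAE assessment at every visit from C1 to C13, and Table 2 counts from the last durvalumab dose. The paired wording therefore most naturally names the regimen.

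**The case against.** The best defence is that the documents still impose the duty. The second bullet of Section 10.4.3 treats the AE that causes a death as the thing to report, so its last sentence could be read as concerning the death alone, with the causal event still reportable under Section 10.4. Section 10.4.1 separately binds the research team to the federal regulations. Late deaths are documented in any case, and the stopping rule is not touched. This shows that a careful reader can reach the right outcome. It does not remove the conflict: Section 10.4 counts death itself as a serious outcome, Post study events names death expressly, and Section 10.4.3 excludes it without qualification. Section 10.4 does let its general SAE duty give way where the protocol states otherwise, but its requirement for related events after 90 days carries no such proviso.

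A second defence concerns Section 10.4.2, which governs communication with supporting companies, while Section 10.4 governs the IND Office and IRB. Different recipients may explain part of the difference, and this stands in part. It is why the new-therapy point is secondary. But Section 10.4.2 words its period generally, and Post study events names both recipients.

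Two stronger readings are tempting. A reader might infer from the differing anchors that the windows lie 48 − 12 = 36 weeks apart. The context set out above does not support that; it is loose wording. A reader might also infer that the new-therapy stop discards a known share of follow-up at substantial drug exposure. The documents give no time to new therapy. The 75–80% in Section 11.3 is a planning assumption about progression, not a rate of switching. The tremelimumab half-life says little about patients who complete treatment, whose last tremelimumab dose was months before their last durvalumab dose.

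**Conclusion.** The contradiction on treatment-related deaths after day 90 is real and can be read directly from the current text. It rests on no numerical assumption, only on reading the last sentence of Section 10.4.3 as written. It is an internal inconsistency in safety reporting, and its consequence is that late related deaths may not be reported as SAEs in a trial whose primary objective is safety. The number of events at risk cannot be estimated from the documents.

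The new-therapy stop, the clock anchor, the progression-death sentence and the start of capture are secondary. Each leaves room for inconsistent practice, and none shows by itself that events will be lost. There is no effect on the 8-week toxicity monitoring.

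**What to change.** Limit the last sentence of Section 10.4.3 to deaths judged not related to study treatment, and refer to Sections 10.3 and 10.4 for related deaths.

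In the same amendment:

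- **New therapy.** State one SAE window across Sections 10.3, 10.4 and 10.4.2, and say how the start of new anticancer therapy bears on it. If the stop in 10.4.2 is meant only for supporting-company reporting, say so.
- **Anchor.** Use one wording for the dose that starts the 90-day clock.
- **Progression deaths.** Repair the first bullet of Section 10.4.3 and make it agree with Sections 10.2 and 10.5.4.
- **Start of capture.** Align consent (Section 10.3) with first protocol-specific intervention (Section 10.4).

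The documents do not show which window was intended, so the sponsor must choose. The cost is a wording amendment, plus a few more SAE reports if the wider window is kept. Table 2 already has AE/SAE contacts at 30 days and 3 months.
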